4.5. Dose Limiting Toxicity (DLT) Definition

A DLT is defined as the occurrence of any of the following toxic reactions that are considered to be causally related to 3D185 by the PI within the first 35 days after the first dose.

- 1. Hematological toxicity:
 - 1. Grade 4 hematologic toxicity;
 - 2. Grade 3 febrile neutropenia (defined as ANC < $1,000/\text{mm}^3$, a single temperature of >

38.3 \mathbb{C} or a sustained temperature of \geq 38 °C for more than 1 hour) or Grade 3 neutropenia

lasts for more than 7 days with or without drug intervention;

3. Grade 3 thrombocytopenia with bleeding or require to platelet transfusion;

- 2. Non-hematologic toxicity:
 - 4. Any Grade ≥ 3 non-hematologic toxicity (except the following conditions that can be controlled by symptomatic treatment within 48 hours: nausea, diarrhea, vomiting, and electrolyte imbalance [except serum phosphorus]; Grade 3 fatigue with duration ≤ 7 days; Grade 3 hypertension that can be self-resolved or controlled by drugs to below 140/90 mmHg or baseline level within 72 hours);
 - 5. Serum phosphorus ≥7 mg/dL that is unable to recover to < 7 mg/dL within 14 days after phosphorus removal;
 - 6. With liver metastasis or baseline transaminase abnormalities: ALT/AST > 8 × ULN; without liver metastasis or baseline transaminase abnormalities: ALT/AST > 5 × ULN ;
 - 7. 3D185-related AEs that resulted in dose interruption of 3D185 for \geq 7 days in the first treatment cycle.

If the DLT is clinically recovered to Grade 0-1 within 28 days, the subject can resume the treatment of 3D185. If the subject can resume treatment, the Investigator may refer to the provisions of Section 6.3 (Precautions and Dose Modifications) for dose modifications to the same dose or reduce by one dose level.

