Grade 3: Severe or medically significant but not immediate sight- threatening; hospitalization or prolongation of existing hospitalization indicated; disabling; limiting self-care ADL	If the toxicity is Grade 3, report as a serious adverse event and permanently discontinue 3D185. If however the toxicity is Grade 3 and reversible (complete resolution or stabilization and asymptomatic) within 4 weeks and the subject is having clinical benefit, and the investigator and the sponsor's medical monitor agree that	
	follow-up or withdraws consent (which ever happens first). If toxicity is Grade 2 and reversible (complete resolution or stabilization and asymptomatic) within 4 weeks according to ophthalmologic examination, resume 3D185 therapy at the next lower dose level after consultation with the medical monitor. In the case of Grade 2 CSR/RPED lasting more than 4 weeks, permanently discontinuing 3D185 ^a .	Follow specific treatment per the ophthalmologist's recommendation.

a. If a subject has been deriving benefit from treatment, and the investigator can demonstrate that reintroduction of study drug is in the best interest of the subject considering the terminal nature of the disease, the drug may be re-introduced at a lower dose and/or intensity if the medical monitor is in agreement with this assessment. With appropriate re-consenting, the subject can be retreated with a 2-dose level reduction as appropriate, along with appropriate clinical follow-up as designated by the investigator. The investigator should also have the subject re-consent, explaining that re-introduction of investigational product could lead to increased risk of recurrent toxicities.

Guidelines for the Management of Dry Eye as follows:

General considerations: Avoid unnecessary exposure to sunlight, use sunglasses in bright light.

Prophylactic management: Frequent use of artificial tear substitutes is strongly recommended.

Reactive management:

20. Withhold 3D185 for grade 3 toxicity, until resolves to Grade 1 or baseline, then

may resume dose level lower. Permanently discontinue 3D185 for grade 4 toxicity

- 21. Artificial tear substitutes if not started, every 4 to 6 hours
- 22. Hydrating /lubricating eye gels and ointments
- 23. Severe treatment-related dry eye should be evaluated by an ophthalmologist

♦ Hepatotoxicity Management Guideline

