6.3.2. Dose Delay/Dose Modification

During the DLT evaluation period of the dose escalation phase, subject can withhold 3D185 due to drug-related AEs. If the withholding time is more than 7 days, the AE will be considered as DLT. Unless DLT occurs, subject's dose of 3D185 will not be reduced during this period.

Treatment can be modified or terminated based on toxicity as described in Table 6. For phosphate, liver, eye, kidney toxicity, specific recommendations in the management guidelines are provided in Section 6.3.1.

Toxicity Grade	Action	Dose Modification After Resolution of Adverse Event
1	None	Continue same dose
2	None or consider withheld or discontinue	If withheld, restart at same dose or 1 dose lower, if necessary.
3	Withheld	Restart at 1 or 2 doses lower if recovery (to \leq Grade 1 or back to baseline for non-hematologic toxicity) is within 28 days. Discontinue drug if unresolved for >28 days.
4	Withheld or discontinue	Discontinue*

Table 6Dose Modification Guidelines

For general toxicity management:

- Subjects with any grade of toxicity (Grade 1 to 4) should be provided symptomatic treatment when applicable.
- Subjects may have more than 1 dose reduction.

- If 3D185 must be withheld for more than 28 days for a drug-related adverse event that fails to resolve to acceptable level (e.g., ≤ Grade 1 non-hematologic toxicity or back to baseline), treatment with 3D185 should be discontinued with the exception noted below.*
- In all cases of clinically significant impaired wound healing or imminent surgery or potential bleeding complications, it is recommended that dose administration be interrupted, appropriate clinical laboratory data be carefully monitored, and supportive therapy administered, where applicable. Dose administration may be restarted when it is considered safe and at an appropriate dose, according to the investigator's assessment.

*Exception: if a subject has been deriving benefit from treatment, and the investigator can demonstrate that re-introduction of study drug is in the best interest of the subject considering the terminal nature of the disease, the drug may be re-introduced at a lower dose and/or intensity if the medical monitor is in agreement with this assessment. With appropriate re-consenting, the subject can be retreated with a 2-dose level reduction as appropriate, along with appropriate clinical follow-up as designated by the investigator.

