6.3.3. Discontinuation criteria for study treatment

When the following 3D185 related severe or life-threatening AEs occur, the investigational product must be permanently discontinued.

- Drug-related Grade 3 AEs or Grade 2 CSR/RPED that cannot recover to Grade ≤ 1 or baseline levels by symptomatic treatment within 28 days;
- Any grade 4 toxicities;
- Recurrent ≥ 2 Grade proteinuria;
- Recurrent Grade 3 eye toxicity associated with vision changes;
- Hy's law confirmed drug-induced liver injury;
- Grade 2 hypercalcemia concurrent with hyperphosphatemia or ≥ Grade 3 hypercalcemia in absence of hyperphosphatemia;
- Other AEs that the Investigator judged to be inappropriate to continue dosing.

If a subject has been deriving benefit from treatment, and the investigator can demonstrate that reintroduction of study drug is in the best interest of the subject considering the terminal nature of the disease, the drug may be re-introduced at a lower dose and/or intensity if the medical monitor is in agreement with this assessment. With appropriate re-consenting, the subject can be retreated with a 2-dose level reduction as appropriate, along with appropriate clinical follow-up as designated by the investigator.

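### Section 4.5 allows a restart at the same dose or one level lower after any recovered DLT, but Section 6.3 calls for a stop or a larger dose cut for some of the same events

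*Protocol*

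**What the plan says.** Section 4.5 closes its DLT list with a general rule: "If the DLT is clinically recovered to Grade 0-1 within 28 days, the subject can resume the treatment of 3D185". The next sentence says that, if the subject can resume, the investigator may consult Section 6.3 "for dose modifications to the same dose or reduce by one dose level". The synopsis carries the same two sentences. Neither excludes any type of DLT.

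The DLT list includes "Grade 4 hematologic toxicity" as its first item, most non-hematologic toxicity of Grade 3 or higher as item 4, and, as item 7, "3D185-related AEs that resulted in dose interruption of 3D185 for" seven days or more in cycle 1.

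Section 6.3 then sets out what to do after toxicity:

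- **6.3.3** lists drug-related events after which "the investigational product must be permanently discontinued". The list includes "Any grade 4 toxicities". A closing paragraph allows re-introduction if the subject is benefiting, the medical monitor agrees and the subject re-consents, with a two-level reduction as appropriate.
- **Table 6 (6.3.2)** gives for Grade 3: "Restart at 1 or 2 doses lower if recovery" occurs within 28 days. For Grade 4, the entry after resolution is to discontinue, subject to the same exception.
- **Table 4 (6.3.1)** covers phosphate above 9.0 mg/dL. The restart is one level lower if phosphate falls below 5.5 mg/dL within 7 days, and two levels lower if that takes 7 to 28 days. Above 10.0 mg/dL the default is a permanent stop.

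**The concern.** Two parts of one protocol answer the same bedside question differently: after this DLT, may the subject go back on drug, and at what dose? Section 4.5 gives the more lenient answer for some events, and its synopsis copy is the text a busy site may read first. Taken literally, it would allow a subject with a recovered Grade 4 hematologic DLT to restart at full dose, where 6.3.3 requires a stop. It would also allow a higher restart dose after severe or slowly resolving toxicity than Tables 4 and 6 give. These subjects have just had a DLT on a drug in early clinical development. Hyperphosphatemia is named in 6.3.1 as a possible toxicity of this drug and a common one for the class, so the phosphate case is foreseeable.

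**Working it through.** The protocol gives no figure to reproduce here. The check sets the two sections side by side for DLTs that settle to Grade 0 or 1 in time. For every row, Section 4.5 offers the same dose or one level lower.

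| DLT | Section 6.3 action | Fit with 4.5 |
|---|---|---|
| Grade 4 hematologic, or any other Grade 4 DLT | Permanent stop (6.3.3, Table 6); re-introduction only under the benefit exception | Neither option fits |
| Phosphate > 10.0 mg/dL | Permanent stop by default; by exception two levels lower (Table 4) | Neither option fits |
| Phosphate > 9.0 mg/dL, recovery in 7 to 28 days | Two levels lower (Table 4) | Neither option fits |
| Phosphate > 9.0 mg/dL, recovery within 7 days | One level lower (Table 4) | Same dose does not fit |
| Grade 3 handled by Table 6 | One or two levels lower | Same dose does not fit; two levels missing from 4.5 |
| Phosphate 7.0 to 9.0 mg/dL | Same dose; reduction possible if persistent (Table 4) | Fits |
| Grade 3 AST/ALT | Same dose if resolved within 7 days; lower dose or investigator's judgment at 7 to 14 days (6.3.1) | Fits |
| Grade 2 event held long enough to be a DLT | Same dose or one lower (Table 6) | Fits |

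**Is phosphate above 9.0 mg/dL a DLT?** Section 8.5.1 grades it as Grade 3. Item 4 of Section 4.5 takes serum phosphorus out of the electrolyte exemption, so it counts. If item 5 were read as the only phosphate rule, a drug-related hold of seven days or more in cycle 1 would still be a DLT under item 7. The two-level case is therefore reached on either reading.

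**Gap in dose.** The preset levels are 25, 50, 100, 150, 200, 250 and 300 mg. Where Table 4 directs two levels lower, the doses 4.5 offers exceed that dose by these ratios:

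| Dose at DLT | Two levels lower | Same dose / two lower | One lower / two lower |
|---|---|---|---|
| 100 | 25 | 100/25 = 4.0 | 50/25 = 2.0 |
| 150 | 50 | 150/50 = 3.0 | 100/50 = 2.0 |
| 200 | 100 | 200/100 = 2.0 | 150/100 = 1.5 |
| 250 | 150 | 250/150 = 1.67 | 200/150 = 1.33 |
| 300 | 200 | 300/200 = 1.5 | 250/200 = 1.25 |

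No preset level lies two below 25 or 50 mg. These ratios describe the dose ladder only, carry no estimate of risk, and would change if the preset levels were adjusted, as Sections 4.4 and 6.2.1 permit.

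**The case against.** The best defense is that 4.5 is permissive and points to 6.3. It says the subject can resume and the investigator may refer to 6.3, whereas 6.3.3 uses mandatory language. A site that obeys 6.3.3 breaches nothing in 4.5. Section 6.3.2 also sends phosphate, liver, eye and kidney toxicity to 6.3.1, so 6.3 is very likely meant to govern. This stands as a reason to call the point minor, but it does not remove the conflict. Section 4.5 states who can resume without exception, then describes 6.3 as offering two options when 6.3 also contains a two-level cut and a stop. The routing in 6.3.2 does not reach Grade 4 hematologic toxicity, and no sentence says that 6.3 overrides 4.5.

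A second objection is that the tables are softer than a list of prohibitions. Table 4 presents itself as general guidance and tells physicians to use clinical judgment. Table 6 is introduced as what can be done, and its Grade 4 action column allows withholding as well as stopping. That also stands. The firmest conflict is therefore the mandatory Grade 4 stop in 6.3.3. The phosphate and Grade 3 conflicts are with recommended actions.

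A reader might also infer that Grade 3 eye toxicity is a plain contradiction, since Table 5 says "If the toxicity is Grade 3, report as a serious adverse event and permanently discontinue 3D185". The protocol does not support that. The same row opens an exception for reversible events with clinical benefit and medical monitor agreement; in the copy I worked from, the row breaks off before any restart dose. The dry-eye guidance separately allows a lower-dose restart after Grade 3. Section 6.3.3 names only recurrent Grade 3 eye toxicity with vision changes, besides Grade 3 events that fail to recover in time. Eye toxicity is mixed and is not counted here.

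**Conclusion.** The contradiction is real and limited to three groups: Grade 4 DLTs; phosphate above 9.0 mg/dL, most clearly with slow recovery or above 10.0 mg/dL; and Grade 3 events governed by Table 6, for which the same dose is not offered. Section 4.5 fits 6.3 for several other DLTs, so it would be wrong to say that the two sections conflict throughout.

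A reader might go further and infer that dose finding is compromised. It is not: the rule applies after a DLT has occurred, so the DLT count, the i3+3 recommendations and the MTD estimate do not change. Nor do the dose ratios show how much harm could follow. The number of subjects affected cannot be derived from the protocol.

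The conclusion assumes that the row above 10.0 mg/dL in Table 4 overrides the row above 9.0, which is the natural reading, and that the sponsor intends 6.3 to prevail. It merits correction as a safety instruction, at low severity.

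**What to change.** In Section 4.5 and the synopsis, replace the two sentences on resuming after a DLT with:

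> If the DLT recovers to Grade 0-1 within 28 days and permanent discontinuation is not required by Section 6.3.3, the subject may resume 3D185. Whether to resume, and the restart dose, are determined by Section 6.3 (6.3.1 for phosphate, eye, liver and kidney toxicity, otherwise Table 6), which takes precedence over this section.

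This deletes the clause naming the same dose or one level lower. It also covers the stop above 10.0 mg/dL, which is in Table 4 and not in the 6.3.3 list. The clinical-judgment wording and the benefit exceptions in 6.3 should stay unchanged; the aim is to settle precedence, not to turn guidance into mandatory rules. The cost is one wording change in two places, with no effect on data collection or the dose-finding design.

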	A DLT is defined as the occurrence of any of the following toxic reactions that are considered to be causally related to 3D185 by the PI within the first 35 days after the first dose.
DLT	1) Hematological toxicity:
	• Grade 4 hematologic toxicity;
	• Grade 3 febrile neutropenia (defined as absolute neutrophil count
	$[ANC] < 1,000/mm^3$, with fever, a single temperature of

$> 38.3 \ \mathbb{C}$ or a sustained temperature of $\ge 38 \ \mathbb{C}$ for more than
1 hour) or Grade 3 neutropenia lasts for more than 7 days with or
without drug intervention;
• Grade 3 thrombocytopenia with bleeding or require to platelet transfusion;
2) Non-hematologic toxicity:
 Any Grade ≥ 3 non-hematologic toxicity (except the following conditions that can be controlled by symptomatic treatment within 48 hours: nausea, diarrhea, vomiting, and electrolyte imbalance [except serum phosphorus]; Grade 3 fatigue with duration ≤ 7 days; Grade 3 hypertension that can be self-resolved or controlled by drugs to below 140/90 mmHg or baseline level within 72 hours);
• Serum phosphorus \geq 7 mg/dL that is unable to recover to
< 7 mg/dL within 14 days after phosphorus removal;
• With liver metastasis or baseline transaminase abnormalities:
ALT/AST > 8 \times ULN; without liver metastasis or baseline
transaminase abnormalities: $ALT/AST > 5 \times ULN$;
• 3D185-related AEs that resulted in dose interruption of 3D185 for
\geq 7 days in the first treatment cycle.
If the DLT is clinically recovered to Grade 0-1 within 28 days, the subject can resume the treatment of 3D185. If the subject can resume treatment,
the Investigator may refer to the provisions of Section 6.3 (Precautions and Dose Modifications) for dose modifications to the same dose or reduce by one dose level.

Specification and	3D185 Tablets: specifications: 50 mg/tablet, 30 tablets/bottle
Administration	Administration: Oral (fast), 28 days per treatment cycle
	Subjects must meet all of the following criteria before they can be enrolled:
	1. Age \geq 18 years.

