6.3. Precautions and Dose Modifications

6.3.1. Precautions

According to preclinical study results of 3D185, the possible toxicity of 3D185 included hyperphosphatemia, liver function abnormalities, gastrointestinal abnormalities, and skeletal system disorders. Based on clinical study results of the similar selective FGFR inhibitors, the common toxicities include hyperphosphatemia, nail and mucosal abnormalities, gastrointestinal abnormalities, ocular abnormalities (including reversible RPED), fatigue, cough, elevated lipase, etc.

Therefore, it must be important to monitor the liver and kidney function, serum phosphate, and skeletal system in this study. The clinical symptoms and signs also should be observed strictly. Once any above abnormalities occur, the Investigator should provide timely and effective medical treatment based on the subject's specific condition.

♦ Hyperphosphatemia & Hypercalcemia Management Guideline

During the study treatment period (including the DLT assessment period), all subjects should restrict phosphate intake to 600-800 mg/day (see Appendix 5 for phosphorus-rich foods). Guidelines for the clinical management of elevated serum phosphate levels are presented in Table 4.

Hypercalcemia is also a known adverse event in patients who received selective FGFR inhibitor treatment. A hypercalcemia should be considered when serum calcium corrected for albumin level is above Upper Limit of Normal (ULN).

In case of grade 2 hypercalcemia concurrent with hyperphosphatemia or grade 3 hypercalcemia in absence of hyperphosphatemia, 3D185 should be discontinued permanently.

Serum Phosphate Level	Dose Modification	Medical Management
5.6-6.9 mg/dL (1.8-2.2 mmol/L)	Continue 3D185 at current dose level.	Restriction of phosphate intake to 600 – 800 mg/day. May consider sevelamer 800 mg to 1,600 mg 3 times a day (with food)
7.0-9.0 mg/dL (2.3-2.9 mmol/L)	Withhold ^a 3D185 treatment until the serum phosphate level returns to < 5.5 mg/dL. Resume at the same dose level. A dose reduction may be implemented for persistent ^b hyperphosphatemia ($\geq 7 \text{ mg/dL}$) if	Restriction of phosphate intake to 600 - 800 mg/day. Sevelamer 800 to 1,600 mg 3 times a day with food until phosphate level is < 5.5 mg/dL.

Table 4Guidelines for Management of Serum Phosphate Elevation

Serum Phosphate Level	Dose Modification	Medical Management
	clinically necessary.	

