> 9.0 mg/dL (> 2.9 mmol/L)	Withhold ^a 3D185 treatment until the serum phosphate level returns to $< 5.5 \text{ mg/dL}$. Resume at the next lower dose level in case of serum phosphate level returns to below 5.5 mg/dL within 7 days. Reduce by two dose levels if it takes 7~28 days to return to below 5.5 mg/dL despite adequate medical management. A second dose reduction may be implemented if needed or clinically indicated for persistent ^b hyperphosphatemia (\geq 7 mg/dL) at every cycle.	Restriction of phosphate intake to 600 – 800 mg/day. Sevelamer up to 1,600 mg 3 times a day with food AND Acetazolamide 250 mg 2 or 3 times a day only until serum phosphate level returns to < 5.5 mg/dL.
> 10.0 mg/dL (> 3.2 mmol/L) or significant alteration in baseline renal function OR Grade 2 hypercalcemia concurrent with hyperphosphatemia	3D185 should be discontinued permanently. (In situations where the subject is having clinical benefit and the investigator and the sponsor's medical monitor agree that re-starting drug is in the best interest of the subject, the drug may be re- introduced at two dose levels lower if appropriate ^c . Follow other recommendations described above.)	Medical management as clinically appropriate.

Note: These are general guidelines that are based on emerging data of other selective FGFR inhibitors and and/or the experts in the field. The treating physicians must use clinical judgment and local standard of care to decide the best way to manage phosphate elevation. If Sevelamer hydrochloride (renagel) is not available, use of other phosphate binders (non-calcium containing) based on the local standard is recommended, including Sevelamer carbonate (Renvela) or lanthanum carbonate (Fosrenol). a. Drug interruptions for hyperphosphatemia suggested to be 7 days duration

b. Persistent hyperphosphatemia is considered to be more than 1 sequential phosphate value of \geq 7 mg/dL c. If a subject has been deriving benefit from treatment, and the investigator can demonstrate that reintroduction of study drug is in the best interest of the subject considering the terminal nature of the disease, the drug may be re-introduced at a lower dose and/or intensity if the medical monitor is in

Serum Phosphate Level	Dose Modification	Medical Management					

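### Section 4.5 and the synopsis misstate the Section 6.3 restart dose for two kinds of recovered DLT

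*Protocol*

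**What the plan says.** Section 4.5 closes with two sentences, repeated in the synopsis. The first sets the recovery condition: "If the DLT is clinically recovered to Grade 0-1 within 28 days, the subject can resume the treatment of 3D185". The second says that the investigator may refer to Section 6.3 for "dose modifications to the same dose or reduce by one dose level".

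Section 6.3 gives these rules:

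- **Table 6 (6.3.2), Grade 3 row:** "Restart at 1 or 2 doses lower if recovery" occurs within 28 days. The same dose is listed only for Grades 1 and 2.
- **Scope of Table 6:** "For phosphate, liver, eye, kidney toxicity, specific recommendations in the management guidelines are provided in Section 6.3.1".
- **Table 4 (6.3.1), phosphate above 9.0 mg/dL:** one level lower if the value is back below 5.5 mg/dL within 7 days; otherwise "Reduce by two dose levels if it takes 7~28 days to return to below 5.5 mg/dL". Above 10.0 mg/dL the default is permanent discontinuation.
- **Table 4, phosphate 7.0 to 9.0 mg/dL:** withhold "until the serum phosphate level returns to < 5.5 mg/dL. Resume at the same dose level".

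Section 8.5.1 grades phosphate as Grade 1 up to 7 mg/dL, Grade 2 up to 9 mg/dL and Grade 3 above that.

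**The concern.** The sentence in 4.5 does more than refer to Section 6.3. It also states what Section 6.3 provides, and for two groups of DLT the statement does not match. Under 4.1 and 6.3.2 the dose may not be reduced during the DLT evaluation period unless a DLT occurs, so this sentence covers the one situation in which a reduction is then allowed.

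An investigator who relies on the summary could restart a subject who has just had a DLT at a higher dose than the governing table gives. Hyperphosphatemia is listed in 6.3.1 as a possible toxicity from the preclinical results and a common one for the drug class, so the phosphate case is not remote.

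**Working it through.** No stated figure needs reproducing. The check compares restart options and then expresses the difference on the dose ladder.

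**Step 1: which DLTs fall where.** Section 6.3.2 sends phosphate, liver, eye and kidney toxicity to the guidelines in 6.3.1. Grade 3 hypercalcemia without hyperphosphatemia is discontinued (6.3.1 and 6.3.3), so it is also outside the Table 6 restart row. Grade 3 febrile neutropenia, Grade 3 thrombocytopenia with bleeding and Grade 3 fatigue lasting more than 7 days are DLTs under 4.5 and remain under Table 6. Phosphate above 9 mg/dL is Grade 3 (8.5.1). Item 4 of the DLT list takes serum phosphorus out of the electrolyte exception, so this value is a DLT. Grade 4 events are not considered here.

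**Step 2: restart options.** Section 4.5 offers the same dose or one level lower.

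| Recovered event | Section 6.3 gives | Against 4.5 |
|---|---|---|
| Grade 3 DLT under Table 6 | one or two lower | 4.5 adds the same dose and omits two lower |
| Phosphate >9.0 to 10.0 mg/dL, 7 to 28 days to <5.5 | two lower | no option in common |
| Phosphate >9.0 to 10.0 mg/dL, within 7 days | one lower | that option is in 4.5 |
| Phosphate 7.0 to 9.0 mg/dL | same dose; reduction possible if persistent | that option is in 4.5 |
| Grade 3 AST/ALT resolved within 7 days | same dose | that option is in 4.5 |
| Proteinuria ≥2 g/24 h, then <2 g/24 h | same or lower dose | agrees |
| Grade 2 event under Table 6, if withheld | same or one lower | agrees |

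Grade 3 eye toxicity under Table 5 is discontinued by default with an exception if reversible, while Grade 3 dry eye may resume at a lower dose. No single range fits every DLT.

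**Step 3: size of the gap.** The levels are 25, 50, 100, 150, 200, 250 and 300 mg (4.1), assuming that a dose level means a preset cohort. No level is preset below 25 mg and no second lower level exists for 50 mg, so those ratios are left out.

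- First case, same dose ÷ one level lower: 50/25 = 2.0; 100/50 = 2.0; 150/100 = 1.5; 200/150 = 1.33; 250/200 = 1.25; 300/250 = 1.2.
- Second case, one level lower ÷ two levels lower, from cohorts 100 to 300 mg: 50/25 = 2.0; 100/50 = 2.0; 150/100 = 1.5; 200/150 = 1.33; 250/200 = 1.25.
- Second case, same dose ÷ two levels lower: 100/25 = 4.0; 150/50 = 3.0; 200/100 = 2.0; 250/150 = 1.67; 300/200 = 1.5.

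Section 4.1 allows an intermediate cohort in a 25 mg step. With one at 275 mg the lowest ratios become 300/275 = 1.09, 275/250 = 1.10 and 300/250 = 1.20; the highest ratios do not change.

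**Step 4: recovery before restart.** Grade 0-1 under 4.5 admits phosphate up to 7 mg/dL. After a hold for phosphate of 7 mg/dL or more, Table 4 requires a value below 5.5 mg/dL. The thresholds differ by 7 − 5.5 = 1.5 mg/dL.

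**The case against.** The strongest reply is that 4.5 names Section 6.3 in the same sentence, so harm requires a reader to ignore the cited section. The language is also permissive: Table 6 is headed as guidelines, and the note to Table 4 says "The treating physicians must use clinical judgment and local standard of care to decide the best way to manage phosphate elevation". In the first case, one level lower satisfies both texts. All of this stands and limits the weight of the point. It does not remove it: consulting 6.3 is worded as optional, and the summary of 6.3 is wrong where it matters. Clinical judgment still needs one consistent default.

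Several stronger readings are tempting but unsupported:

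- **That 4.5 is wrong for DLTs in general.** The table in the working shows several events for which its wording fits.
- **That every toxicity outside the four organ guidelines restarts under Table 6.** Grade 3 hypercalcemia is discontinued.
- **That the 1.5 mg/dL difference means dosing at levels Table 4 forbids.** Table 4 lets dosing continue unchanged at 5.6 to 6.9 mg/dL when there has been no hold. It is stricter only on restart after one.
- **That the Grade 0-1 sentence should go, leaving recovery wholly to 6.3.** Table 6 states its Grade 3 recovery threshold only for non-hematologic toxicity and gives none in the Grade 2 row. Section 6.3.3 is a 28-day stopping rule that also accepts return to baseline. Deleting the sentence would loosen restart after hematologic DLTs and after DLTs defined by a dose interruption of 7 days or more.

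**Conclusion.** The point holds for two cases: recovered Grade 3 DLTs governed by Table 6, and phosphate above 9.0 and up to 10.0 mg/dL with recovery in 7 to 28 days. The mismatch in the phosphate level before restart is a lesser point.

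The ratios describe the distance between the two texts on the preset ladder. They are not an estimate of harm, and the number of subjects affected cannot be derived from the protocol.

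A reader might infer that dose finding is compromised. It is not: restart follows a DLT that has already been counted, so DLT counts, i3+3 decisions and MTD selection do not change. This is an internal inconsistency in a safety instruction that should be corrected, not a flaw in the design.

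**What to change.** Make the same change in Section 4.5 and in the synopsis:

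1. Keep the sentence requiring recovery to Grade 0-1 within 28 days, and add: *unless Section 6.3 requires stricter recovery or discontinuation for that toxicity*.
2. Replace the next sentence with: *If the subject can resume treatment, the restart dose is as specified for that toxicity and grade in Section 6.3 (Tables 4-6 and the organ guidelines)*. This removes the phrase that names the same dose or one level lower.

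The cost is two edited sentences in two places, with no change to design, sample size or data collection.
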